10.9.1 Objective

To assess the pharmacokinetics (PK) of MOR00208.

10.9.2 Endpoint: MOR00208 plasma concentrations at sampling timepoints, accumulation ratios and trough concentrations

10.9.3 Analysis

The main analysis will be conducted on the PKAS. Individual plasma samples for the analysis of MOR00208 PK will be collected on various study days. For evaluation of PK metrics, a patient subsample will be considered consisting of those patients who have at least one quantifiable MOR00208 serum concentration (the PK analysis set, PKAS).

30.1.1 *Bioanalytical assessment of pharmacokinetic serum samples*

MOR00208 concentration values for each serum sample are to be determined using a validated Ligand Binding Assay. A separate bioanalytical phase plan and report will be generated that provide details on samples handling and processing, methods used for sample analysis, statements on quality control/quality assurance (QC/QA) and results of the each individual sample analyzed for each patient by the bioanalytical labs.

31.1.1 *Data analysis*

MOR00208 serum concentrations will be summarized based on nominal (scheduled) sampling times. Serum concentrations below the limit of quantification or missing data will be labelled as such in the concentration data listings. Analyte concentrations that are below the limit of quantification (BLQ) will be assigned a value of zero when they precede the first quantifiable sample. All other BLQ samples will be treated as missing data. Summary statistics for MOR00208 serum concentrations will include n, arithmetic mean, StD, geometric mean, coefficient of variation (CV), median, minimum and maximum. The CV will be expressed as a percentage and calculated as follows:

-
- CV of the arithmetic mean (%) = $\text{StD}/\text{mean} * 100$.
 - CV of the geometric mean (%) = $\sqrt{\text{exp}(\text{variance for log transformed data}) - 1} * 100$.

Concentration figures (linear and log y-axis) of mean concentrations +/- StD will be presented. Individual MOR00208 serum concentrations may be excluded from summary statistics and concentration figures (mean) if the actual collection time/date of the sample exceeds allowable windows relative to the scheduled collection time/date.

- For samples collected 1h after the end of MOR00208 infusion, results will be excluded from summary statistics if the deviation of the actual collection time is larger than ± 15 min from the scheduled collection time.
- Results of PK samples collected outside of the allowed window of ± 1 day relative to the scheduled collection day will be excluded from summary statistics. Each 28 day cycle will be considered separately.

Irrespective of exclusion of data points from summary statistics, each obtained MOR00208 serum concentration will be listed and reported.

Accumulation of MOR00208 will be investigated by comparing the average concentration of pre-dose and 1 hour post-dose of Cycle 3 Day 1 (i.e. the 10th dose) with the corresponding mean from the previous visit for which MOR00208 concentration data is available using ANOVA ($\alpha = 0.05$). If no significant difference is found, Cycle 3 Day 1 will be compared to previous visit for which MOR00208 concentration data is available and so forth until two consecutive times a significant difference is found.

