6.6.2 Management of Toxicities

The next cycle of treatment may begin on the scheduled Day 1 if:

- ANC is $\geq 1.000/\text{mm}^3$ (unless neutropenia is due to infiltration of bone marrow)
- Platelets $\geq 50000/\text{mm}^3$ (unless thrombocytopenia is due to infiltration of bone marrow, patient may have received transfusion) and absence of active bleeding
- No serious organ or other toxicity present.

If, based on medical judgment, the treating physician considers a change in laboratory parameter or AE not to be a study drug-related toxicity, but to represent a natural fluctuation in or progression of the underlying disease, then it is at the physician's discretion and assessment of the individual risk/benefit ratio to determine whether the patient should be dosed. The decision and rationale behind the decision should be documented in the source data.

If the above conditions are not met on Day 1 of a new cycle, the subject will be evaluated once every seven days and a new cycle will not be initiated until the toxicity has resolved as described above. Specific course of action for a given toxicity occurring in the course of the treatment cycle is described below.

If treatment needs to be interrupted for ≤ 28 days for the same study drug-related toxicity, the patient's treatment should continue, depending on the duration of treatment interruption, at the next protocol scheduled visit. No missed visits or doses of either drug should be made up.

If treatment with one study drug needs to be interrupted for >28 days for the same, persistent, drug-related toxicity, the study drug judged by the investigator to have caused the toxicity should be discontinued and the patient should continue to be dosed with the other study drug, as per protocol.

If treatment with both study drugs needs to be interrupted for >28 days for the same persistent study drug-related toxicity, judged by the investigator to be related to both study drugs (LEN and MOR00208), then the End of Treatment Visit will be performed and the patient will enter the follow-up phase (see [Section 5.3.1](#)).

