MOR00208 administration	X	X	X	X	X	X	X	X	X	X	X	X	
LEN tablets allocation	X		X		X		X		X		X		
(S)AE assessment	X	X	X	X	X	X	X	X	X	X	X	X	
PK MOR00208	X ¹			X ¹				X ¹					
Second primary malignancy	X	X	X	X	X	X	X	X	X	X	X	X	

Schedule: Additional Treatment Period and Follow-Up Period

Evaluation or Procedure	MOR00208 Additional Treatment Phase (28 Days Cycles #13–24) (First cycle of additional treatment possible up to 2 weeks ±2 days after Cycle 12 Day 28)		MOR00208 Additional Treatment Phase ^{19, 20} (28 Days Cycles #25 onwards)		Unscheduled Visit (in case MOR00208 is to be administered despite disease progression) ⁸	End of Treatment Visit (EOT)	30 Day Follow-up Visit	Survival Follow-up ⁹ (every 3 months ±2 weeks from last visit by phone)
Day	D1 ±2 days	D15 ±2 days	D1 ±2 days	D15 ±2 days		(assessments can take place within 7 days period of the actual visit)	±2 days	
Previous/concomitant medication ¹⁰	X ¹⁷	X ¹⁷	X ¹⁷	X ¹⁷	X	X		
Full physical examination (Limited physical examination - L)	L ^{11, 17}		L ^{11, 17}		X	X	L	
ECOG performance status					X	X		
Body weight/height ²	X	X	X	X	X	X		
Vital signs	X	X	X	X	X	X		
B-symptoms	X ¹⁷				X	X	X	
12-lead resting ECG					X	X		
Urinalysis ¹⁸	X ¹⁷				X ¹⁸	X ¹⁸		
Pregnancy test (FCBP) ⁴	X ¹		X ¹		X ¹⁸	X ¹⁸		
“Emergency laboratory” ⁵	X	X	X	X				
Central laboratory blood sampling ^{1, 18}	X ¹⁷				X ¹⁸	X ¹⁸		
Serology (Hepatitis B) ¹⁸	X ^{16, 17}				X ^{16, 18}	X ^{16, 18}		
Anti-MOR00208 antibodies	X ^{1, 12, 17}					X ¹⁸		
CT or MRI scan for tumour measurement and disease	X ^{13, 17}		X ^{13, 17}					

Evaluation or Procedure	MOR00208 Additional Treatment Phase (28 Days Cycles #13–24) (First cycle of additional treatment possible up to 2 weeks ±2 days after Cycle 12 Day 28)		MOR00208 Additional Treatment Phase ^{19, 20} (28 Days Cycles #25 onwards)		Unscheduled Visit (in case MOR00208 is to be administered despite disease progression) ⁸	End of Treatment Visit (EOT)	30 Day Follow-up Visit	Survival Follow-up ⁹ (every 3 months ±2 weeks from last visit by phone)
Day	D1 ±2 days	D15 ±2 days	D1 ±2 days	D15 ±2 days		(assessments can take place within 7 days period of the actual visit)	±2 days	
assessment (local)								
Disease and disease response assessment (CT/PET)			X ^{17, 19}		X ^{13, 14}	X ^{13, 14, 17}		
Bone marrow aspiration & biopsy		X ^{7, 15, 17}						
MOR00208 administration	X	X	X	X				
(S)AE assessment	X	X	X	X	X	X	X	
PK MOR00208	X ^{1, 12, 17}					X ¹⁸		
Second primary malignancy	X	X	X	X	X	X	X	X

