Antineoplastic therapy other than the study drug treatment ²¹	X ²¹	X ²¹	X ²¹	X ²¹	X ²¹	X ²¹	X ²¹	X

Abbreviations: ADCC=antibody-dependent cell-mediated cytotoxicity; AE=adverse event; β-HCG=beta-human chorionic gonadotropin; CT=computed tomography; ECG=electrocardiogram; ECOG=Eastern Cooperative Oncology Group; FCBP=female of childbearing potential; IPI= International Prognostic Index; IV = intravenous; L= Limited physical examination; LEN=lenalidomide; MRI=magnetic resonance imaging; NK=natural killer; PET=positron emission tomography; PK=pharmacokinetics; SAE=serious adverse event.

¹Before study drug administration.

²Body height will be measured at Cycle 1 Day 1 only. Body weight can be measured up to 24 hours prior to the study drug administration.

³12-lead resting ECG performed no later than 3 hours post-MOR00208 dose (see [Section 7.2.10](#)).

⁴Pregnancy tests: for FCBP, two pregnancy tests must be performed before enrolment; the first, a serum pregnancy test at screening within 10 to 14 days prior to the start of study drug and the second, a medically supervised urine pregnancy test within 24 hours prior to the start of study drug. The results of both tests must be negative in order to receive Cycle

¹ Day 1 dosing. At all other indicated time points, a urine pregnancy test for FCBP will be performed locally and the result must be negative for dosing. A β -HCG pregnancy test should also be performed at the End of Study Visit.

⁵Sample to be collected and evaluated in the local laboratory (up to 24 hours prior to study drug administration) and reviewed by study treating physician before study drug administration.

⁶MOR00208 PK sample will be taken pre-dose and 1 hour \pm 10 min after the end of MOR00208 infusion.

⁷Repeat bone marrow biopsy to confirm a CR only in those patients who had known bone marrow involvement prior to dosing (see [Section 7.2.14.2](#) for details).

⁸For patients receiving antibody treatment despite disease progression / relapse, an **Unscheduled Visit** covering all assessments described under EOT visit should be completed (except PK sample) before the continuation of antibody therapy. These procedures, if performed within less than two weeks preceding this visit, need not be repeated. PET/CT need not be repeated if it was performed during previous treatment cycle.

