⁹After 30-Day Follow-up Visit, a call will be made to the patient (or the patient's family) every 90 days for at least 5 years from Cycle 1 Day 1 to inquire about the patient's status, second primary malignancy (SPM) and information on any antineoplastic therapies utilised since discontinuation of study treatment.

¹⁰After disease progression has been recorded, only anticancer treatments and, in case of an AE, other relevant concomitant medications (at the discretion of the investigator) should be entered. Before and up to the End of Treatment Visit, the complete concomitant medication needs to be recorded.

¹¹A limited PE (L) will be performed on Day 1 of each Cycle, every 12 weeks \pm 2 days from the previous PE.

¹²Anti-MOR00208 antibody sample and MOR00208 PK sample (pre-dose only) will be taken in odd numbered additional treatment cycles only (i.e. treatment Cycles 13, 15, 17, 19, 21, 23). No samples to be collected after Cycle 23.

¹³Disease assessment by CT/MRI of neck, chest, abdomen & pelvis with iv contrast during additional treatment phase; Cycles 13-24: approximately every 3 months \pm 2 days from the previous scan. First assessment during this phase can be done directly 3 months after Cycle 12 D28 PET/CT assessment. Thus, this assessment is not needed at Cycle 13 Day 1, and an interval longer than \sim 3 months is acceptable for Cycle 16 Day 1 assessment; Cycle 25 onwards: approximately once every year \pm 2 weeks from the previous scan. Images will have to be transferred to the central imaging laboratory.

¹⁴In case the patient is withdrawn from treatment before the end of Cycle 12 for reasons other than progression of disease. PET/CT is only required at the EOT visit if it was not performed in the cycle before the end of treatment visit.

¹⁵Bone marrow assessment during additional treatment phase (Cycles 13 to 24) approximately every 3 months \pm 2 weeks from the previous assessment; to be performed to confirm a CR only in those patients who had known bone marrow involvement prior to dosing. Refer to [Section 7.2.14.2](#) for further details.

¹⁶HBV-DNA to be measured and re-measured only if anti-HBc was positive at screening. If HBV-DNA is positive at screening, or during treatment, please see [Section 7.2.13.2](#).

¹⁷Not applicable for patients who continue receiving MOR208 despite disease progression.

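### From Cycle 4 the SAP's PK window is narrower than the protocol's visit window, and no rule checks that a pre-dose sample is a regular trough; the trough summaries may be biased by an unknown amount

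*SAP*

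**What the plan says.** SAP 10.9.2 names trough concentrations among the PK endpoints for secondary objective 9. SAP 10.9.3 (Data analysis) summarises serum concentrations by nominal sampling time and gives these handling rules:

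- The lead-in is permissive: individual values "may be excluded from summary statistics and concentration figures (mean) if the actual collection time/date of the sample exceeds allowable windows".
- The day rule is firm: samples "collected outside of the allowed window of ± 1 day relative to the scheduled collection day will be excluded from summary statistics".
- The reference for the scheduled day is described only by "Each 28 day cycle will be considered separately".
- BLQ results are set to zero before the first quantifiable sample. After that, "All other BLQ samples will be treated as missing data".
- Every concentration is listed, whether or not it is summarised.

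On the protocol side, Table 5 gives ±1 day for the windowed visits of Cycles 1–3 and ±2 days for Day 1 and Day 15 from Cycle 4. PK sampling continues after Cycle 3. Cycles 4–6 have a pre-dose sample on Day 1, and in the additional treatment phase a "MOR00208 PK sample (pre-dose only) will be taken in odd numbered additional treatment cycles only", up to Cycle 23. The End of Treatment visit also has a PK sample, with its own 7-day allowance. Table 5 also permits a gap before Cycle 13: "First cycle of additional treatment possible up to 2 weeks ±2 days after Cycle 12 Day 28". Protocol 6.6.2 provides for interruption of study drug for toxicity and adds: "No missed visits or doses of either drug should be made up".

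**The concern.** The SAP calls ±1 day the allowed window, but from Cycle 4 the protocol allows more. A patient seen, dosed and sampled in full compliance could be left out of the by-visit summary, and no reason is given for the tighter limit.

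The rule also tests the calendar day, whereas a trough is defined by time since the last infusion. Once infusions can be skipped and are not replaced, a sample can fall on the right day and still not be a trough of the 14-day regimen.

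Finally, setting later BLQ values to missing takes the lowest results out of the mean.

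At stake is the descriptive table for a named secondary endpoint: whether it describes exposure on the planned schedule. No efficacy result depends on it.

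**Working it through.** **The plan's own figure.** SAP 10.9.3 calls Cycle 3 Day 1 the 10th dose. Cycle 1 has 5 infusions (Days 1, 4, 8, 15, 22), Cycle 2 has 4, and the next is 5 + 4 + 1 = 10. It reproduces.

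**1. Windows side by side.**

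| Period | Protocol Table 5 | SAP 10.9.3 | Difference |
|---|---|---|---|
| Cycles 1–3 | ±1 day (none shown for Cycle 1 Days 1 and 4) | ±1 day | none |
| Cycle 4 onward | ±2 days on Days 1 and 15 | ±1 day | 1 day each side |
| End of Treatment | 7-day allowance | no specific rule | undefined |

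The samples at risk from Cycle 4 are those at exactly ±2 days. The documents give no visit-day spread, so their share is an assumption:

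- uniform over −2 to +2: 2/5 = 40%
- triangular weights 1-2-3-2-1: 2/9 = 22%
- peaked weights 1-2-14-2-1: 2/20 = 10%

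These shares apply if the scheduled day comes from the planned calendar. If each cycle is counted from its own actual Day 1, a Day 1 sample has zero deviation and none is lost; only a Day 15 sample could be. The column positions of the PK marks for Cycles 7–12 are not certain in the text of Table 5, so I do not size a Day 15 loss.

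**2. Time since the last infusion.** The nominal interval from Cycle 4 is 14 days. Two cases pass the day rule:

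- *Omitted infusion.* Cycle 4 Day 15 is skipped and Cycle 5 Day 1 is on time. The pre-dose sample comes 28 days after the last infusion and passes under either anchor.
- *Permitted late Cycle 13.* From Cycle 12 Day 15 to Day 28 is 13 days. Adding 14 gives 27, and adding the 2-day tolerance gives 29. This passes if the cycle is counted from its own Day 1.

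The documents give no half-life. Assume first-order decay, steady state every 14 days, and a half-life t of 7–28 days:

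| t (days) | 2 days late, 2^(−2/t) | One infusion omitted, 2^(−14/t) |
|---|---|---|
| 7 | 0.82 | 0.25 |
| 14 | 0.91 | 0.50 |
| 21 | 0.94 | 0.63 |
| 28 | 0.95 | 0.71 |

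So the sample that may be excluded is 5–18% below the regular trough, and the one that can be kept is 29–75% below it. If a fraction f of the summarised samples follows an omitted infusion, the mean falls by f × (1 − ratio). For f = 5% and t = 28 this is 0.05 × 0.29 = 1.5%; for f = 20% and t = 7 it is 0.20 × 0.75 = 15%. Both values of f are assumptions.

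**3. BLQ set to missing.** If a share b is BLQ with true values near zero, the reported mean is 1/(1 − b) times the true mean: 1.01 at b = 1%, 1.05 at 5%, 1.11 at 10%, and unchanged at 0%. No BLQ rate is given.

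**Direction.** Omitted infusions lower the mean trough, BLQ handling raises it, and the window mainly costs sample size.

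**The case against.** The best reply is that these are descriptive summaries by nominal time. Including patients with skipped doses describes exposure as treated, which is legitimate. All values are listed, BLQ results are labelled in the listings, and sources of PK variability, including anti-drug antibodies, are assigned to a separate population PK analysis. The lead-in also says values may be, not must be, excluded. If each cycle is counted from its own Day 1, the window conflict largely disappears for Day 1 samples.

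Much of this stands. The listings and the population analysis limit the harm, and the window conflict does not touch the Cycle 3 Day 1 accumulation comparison, because the windows agree up to that point. However, neither the listings nor the separate analysis corrects the by-visit table for objective 9. Own-Day-1 counting removes the window problem for Day 1 samples only by giving them zero deviation after any delay, so the rule then screens nothing there. Nor does an as-treated summary fit an endpoint named as trough concentration unless the text says so.

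A reader might also infer that the SAP deliberately retains samples after omitted infusions, or deletes all BLQ values. It does neither: retention follows from the absence of a criterion, and BLQ values before the first quantifiable sample are set to zero.

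**Conclusion.** The concern holds in a limited form. From Cycle 4 the SAP window is one day tighter on each side than the protocol's, so compliant samples may be excluded; the anchor day that decides how many is undefined. No stated criterion removes or flags a pre-dose sample after an omitted infusion or a permitted late Cycle 13 start. BLQ values after the first quantifiable one are dropped, which can only raise the mean.

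A reader might conclude that the reported trough profile is distorted, or that 40% of later samples will be lost. The documents support neither. The 40% needs calendar anchoring and an even spread of visit days; other assumptions give 22%, 10% or about none. The biases run in opposite directions, and the half-life, omission rate, BLQ rate and visit spread are all absent. What can be said is that the rules may bias the Cycle 4 onward trough summaries by an amount that cannot be computed from the documents, and that they can discard a small deviation while keeping a larger one. This is worth correcting because it is cheap; it does not bear on the primary endpoint.

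**What to change.** Amend SAP 10.9.3:

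- **(a) Window.** Use the protocol visit window for scheduled visits: ±1 day in Cycles 1–3 and ±2 days from Cycle 4. State the day from which the schedule is counted, add a rule for the End of Treatment sample, and use either may or will for exclusions throughout.
- **(b) Trough.** For the trough summary, include a pre-dose sample only if the preceding scheduled infusion was given and the elapsed time lies in the range the protocol windows permit. Two weekly visits at ±1 day are 7 ± 2, or about 5–9 days, apart; two 14-day visits at ±2 days are 14 ± 4, or 10–18 days, apart. Limits of 7 ±1 and 14 ±2 would exclude compliant visits. Handle the early doses and the weekly-to-14-day transition explicitly. Flag and list the rest, including a late Cycle 13 Day 1, as non-trough.
- **(c) BLQ.** Report the number and percentage BLQ per visit. Add a sensitivity summary with BLQ values after the first quantifiable sample set to half the lower limit of quantification.

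The cost is SAP wording and a little programming. Summary means may shift slightly in either direction: (b) tends to raise them, and the sensitivity summary in (c) to lower them.

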10.6.2.5 Pharmacokinetic Analysis

Appropriate PK parameters for MOR00208, with a focus on, but not limited to, accumulation ratios, will be computed based on non-compartmental data analysis and summarised using descriptive statistics. Mean concentrations (on original and on log-linear scale) will be visualised in figures. Further details of the PK analysis will be specified in the SAP.

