5.3 Determination of sample size

Approximately 80 patients with R-R DLBCL who meet all of the inclusion criteria and have none of the exclusion criteria will be enrolled into the study. The study will be performed with an interim stop for the evaluation of the safety of the LEN dosage. No adjustment of sample size or adaptation of efficacy evaluations will be made at this point. As the primary purpose of this study is to evaluate the clinical efficacy of 25 mg daily oral LEN combined with 12 mg/kg MOR00208 administered by IV infusion in patients with R-R DLBCL, no formal statistical hypothesis testing will be performed.

**STATISTICAL ANALYSIS PLAN**MorphoSys AG
MOR208C203

For the determination of a suitable sample size, it is assumed that the combination treatment could improve the ORR of LEN from a value of 20% (under monotherapy) to 35% (under combination therapy). Applying an exact binomial test with a two-sided significance level of 5% and a power of 85% the estimated sample size is 73 patients (calculation performed by nQuery Advisor® 7.0). According to this scenario an observed ORR of 32% would lead to the conclusion that the outcome is statistically superior to outcomes observed previously for the monotherapy. Assuming a drop-out rate of 10%, a total sample size of about 80 patients is estimated.

The sample size determination has been conducted using various possible monotherapy and combination effect ORR rates and various power assumptions. Literature evaluation of study results concerning the ORR rates of LEN or comparable products (as mono- or combination therapy) as well as study results for MOR00208 ongoing studies were used to justify assumptions on response rates (Witzig et al., 2011; Wang et al., 2013).

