8.9 Study treatment

8.9.1 Treatment cycles

The patients will be administered study treatment according to cycles. Each Treatment cycle will consist of 28 days. The duration of exposure for each study treatment drug is defined according to regimen as outlined below.

MOR00208:

The planned administration of MOR00208 is as follows:

- Cycle 1: Day 1, Day 4 (loading dose), Day 8, Day 15, Day 22.
- Cycle 2: Day 1, Day 8, Day 15, Day 22.
- Cycle 3: Day 1, Day 8, Day 15, Day 22.
- Cycle 4 onwards: Day 1 and Day 15.

MOR00208 will be administered at a dose of 12.0 mg/kg IV. Dose reductions of MOR00208 are not allowed during the course of the study. Unless contraindicated the MOR00208 treatment should continue, even if the patient discontinues LEN treatment.

LEN:

The planned administration of LEN is as follows:

- Cycle 1 to Cycle 12: 25 mg oral LEN daily on days 1-21 of the respective cycle.
- Reduced LEN doses after reduction of the total daily dose (see Section 8.9.3) will also be administered on days 1-21 until Cycle 12.

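### The MOR00208 accumulation analysis steps back through visits on non-significant ANOVAs with no stated patient term, margin, interval or interpretation, and the named accumulation ratio has no formula

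*SAP*

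**What the plan says.** SAP 10.9.3, under its data analysis subsection, says accumulation will be "investigated by comparing the average concentration of pre-dose and 1 hour post-dose of Cycle 3 Day 1 (i.e. the 10th dose"), against the "corresponding mean from the previous visit for which MOR00208 concentration data is available". The test is an ANOVA at alpha 0.05. The continuation rule is: "If no significant difference is found, Cycle 3 Day 1 will be compared to previous visit for which MOR00208 concentration data is available". Stepping back then carries on in the same way, with the end point worded as "and so forth until two consecutive times a significant difference is found".

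The text stops there. It does not say what conclusion follows from the visit reached, which terms the ANOVA contains, whether concentrations are logged, or how patients with data at only one of the two visits are handled. What to do after a single significant result is only implied.

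Elsewhere the plan promises more. Protocol 10.6.2.5 says PK parameters will be computed, "with a focus on, but not limited to, accumulation ratios", and leaves further detail to the SAP. SAP Table 1 (objective 9) and the endpoint heading in 10.9.2 both name accumulation ratios. SAP 7.2 lists descriptive statistics for PK parameters, including the geometric mean and geometric CV. SAP 10.9.3 also plans a population PK analysis under its own protocol. None of these places gives a formula, reference visit or confidence interval for the accumulation ratio.

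**The concern.** A rule that moves on whenever a test fails to reach significance uses absence of evidence as its working signal. With no margin and no interval, a small or noisy data set produces more non-significant steps, and so a different stopping visit, than a large precise one with the same underlying pharmacokinetics. The output is a visit label, not an amount of accumulation.

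The model matters as much as the sample size. The same patients are sampled at each visit, so a comparison that removes between-patient variation behaves quite differently from one that leaves it in the error term. Two programmers could both follow the text and reach different answers. The PK analysis set (SAP 6.13.6) requires only one quantifiable concentration, so the handling of incomplete pairs also needs a rule.

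Pooling pre-dose and 1-hour post-dose values blurs trough, which SAP 10.9.2 names as an endpoint in its own right, with near-peak. The two need not accumulate to the same degree.

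At stake is the quality of the answer to secondary objective 9.

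**Working it through.** **The plan's own figure.** SAP 8.9.1 gives "Cycle 1: Day 1, Day 4 (loading dose), Day 8, Day 15, Day 22" (five doses), then four in Cycle 2. Cycle 3 Day 1 is therefore dose 5 + 4 + 1 = 10, as SAP 10.9.3 states. No sample size, power, effect size or margin is given for the accumulation comparison, so there is nothing else to reproduce.

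**Inputs from the documents.** Alpha is 0.05 per comparison. SAP 5.3 sets the ceiling on patients: "Approximately 80 patients with R-R DLBCL who meet all of the inclusion criteria". The Protocol schedule of assessments, whose table is partly broken, appears to place paired pre-dose and 1-hour samples at Cycle 1 Days 1, 4 and 15 and Cycle 2 Days 1 and 15, giving up to five comparisons.

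**Assumed inputs.** The documents give no SD, CV, correlation or number of complete pairs. Steps 1 and 2 assume n = 70, between-patient log-SD (s_b) 0.35 to 0.45 and within-patient log-SD (s_w) 0.15 to 0.20.

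**Step 1: one comparison, by formula, at mid-range** (s_b = 0.40, s_w = 0.175, true ratio 1.10, log 1.10 = 0.0953).

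- Standard error used by an ANOVA without a patient term: √[2(s_b² + s_w²)/n] = √[2(0.1600 + 0.0306)/70] = 0.0738. It rejects when the log difference exceeds 1.977 × 0.0738 = 0.146.
- Actual standard error of the within-patient difference: √(2s_w²/n) = √(2 × 0.0306/70) = 0.0296.
- Power without a patient term: P(Z > (0.146 − 0.0953)/0.0296) = P(Z > 1.71), about 4%.
- Power of the paired test: P(Z > 1.995 − 0.0953/0.0296) = P(Z > −1.23), about 89%.

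These figures treat the estimated standard error as fixed. The simulation in step 2 does not.

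**Step 2: the same comparison simulated over the assumed range.**

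| True ratio | Significant, no patient term | Significant, paired |
|---|---|---|
| 1.00 | about 0% | about 5% |
| 1.10 | 1% to 13% | 79% to 96% |
| 1.20 | about 70% to 98% | over 99% |

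**Step 3: the stepwise rule on one fixed true profile.** Assumptions: weekly dosing with the Day 4 dose, mono-exponential decline with half-life 14 days, CV 50%, within-patient correlation 0.7, log scale, 4,000 runs. Each visit's average is proportional to Σ 2^(−(t−x)/14) over earlier doses x, plus half of one dose increment. The true ratios of Cycle 3 Day 1 to Cycle 2 Day 15, Cycle 2 Day 1 and Cycle 1 Day 15 are then 1.03, 1.09 and 1.24. The rule was run until two consecutive significant results. The table shows the earliest visit still not significantly different.

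| n, model | C1 D15 | C2 D1 | C2 D15 | None |
|---|---|---|---|---|
| 30, no patient term | 66% | 33% | 2% | 0% |
| 30, paired | 12% | 64% | 20% | 3% |
| 80, no patient term | 6% | 86% | 8% | 0.3% |
| 80, paired | 0.2% | 45% | 46% | 9% |

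The pharmacokinetics are identical in every row. Only n and the model change.

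**Step 4: multiplicity.** Five unadjusted tests give 1 − 0.95⁵ = 22.6% chance of at least one false positive if independent. Simulated paired tests sharing Cycle 3 Day 1 gave 19%.

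**The case against.** Four points can fairly be made for the plan.

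- A reader might infer that the SAP equates non-significance with steady state. It does not say so: the section describes a sequence of comparisons and draws no conclusion. What stands is the gap itself, since a rule with no stated interpretation cannot be reported consistently.
- A reader might infer that pairing is ignored. The word ANOVA does not exclude a repeated-measures model or a patient term. If one is used, the low figures in the unpaired columns do not apply. What stands is that the choice is left open and changes the result.
- A reader might infer that the test is simply underpowered. The documents give no variance or effect size from which to conclude that. No document calls a 10% rise important, and a 20% rise is usually detected even without a patient term.
- A reader might infer that accumulation rests on this test alone. Individual ratios, their descriptive summaries and a population PK analysis are also planned, and an approximate interval could be built from n, the geometric mean and the geometric CV. That helps only once the ratio is defined. The population analysis pools other trials, is reported separately, and its description does not mention accumulation.

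It is also true that no dosing or stopping decision in the documents is tied to this analysis.

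**Conclusion.** The point holds in a limited form. The SAP states a stepwise rule driven by non-significance, on a pooled trough and 1-hour average, with no stated patient term, margin, confidence interval or interpretation. Its stopping visit therefore reflects sample size and an unspecified model as well as the drug. The accumulation ratio the protocol puts first has no formula, reference visit or interval.

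The size rests on assumed variances, correlation and half-life. Under them, the choice of model moves power for a 10% rise from roughly 1% to 13% up to 79% to 96%, while for a 20% rise the loss is modest to small. The documents do not support the stronger readings that the plan declares steady state from a null result, that it rules out pairing, or that low power is inherent.

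This is a secondary PK analysis. ORR is unaffected. It is worth changing because the remedy is cheap and delivers the endpoint already named.

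**What to change.** Replace the stepwise test in SAP 10.9.3 with a linear mixed model for log concentration, visit as fixed effect and patient as random effect, fitted separately to trough and 1-hour post-dose values. All available visits contribute, so incomplete pairs need no separate exclusion rule.

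Report geometric mean accumulation ratios with 90% confidence intervals, each visit against a named reference visit and against the previous PK visit. Describe accumulation by the size of the ratio and its interval, not by a significance label.

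The reference for trough must be a visit with a quantifiable pre-dose value. It cannot be Cycle 1 Day 1 pre-dose, because SAP 10.9.3 sets values below quantification to zero when they precede the first quantifiable sample, and zero has no logarithm. Cycle 1 Day 15 is one candidate, since its pre-dose sample follows a 7-day interval like the later weekly visits. Write out the ratio formula and the numerator and denominator visits.

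As a guide to precision, with 50 complete pairs, an assumed CV of 50% and correlation 0.5, a 95% interval runs from the ratio divided by 1.14 to the ratio times 1.14; a 90% interval is narrower.

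Cost: one SAP paragraph and one model on samples already collected.
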